- Continuity in readings of fetal heart rate (as measured in the number of minutes without a readable tracing in a 30 minute sample tracing) between EUM and fetal scalp electrode and external fetal heart rate monitoring from the same patient
- Continuity in readings of contractions (as measured in the number of minutes without a readable tracing in a 30 minute sample tracing) between EUM, IUPC and external tocodynamometer from the same patient

Secondary Outcomes:

- Compare average frequency of contractions between the monitoring systems
- Compare duration of contraction between the monitoring systems
- Compare maximum height of the contraction between the monitoring systems
- Compare total Montevideo units obtained between the monitoring systems
- Compare the timing of the contraction between the monitoring systems
- Compare average fetal heart rate between the monitoring systems
- Compare baseline heart rate between the monitoring systems
- Compare the number accelerations between the monitoring systems
- Compare the number of decelerations between the monitoring systems
- Compare the timing of the accelerations between the monitoring systems
- Compare the timing of decelerations between the monitoring systems
- Compare the maximum fetal heart rate achieved during acceleration between the monitoring systems
- Compare the lowest fetal heart rate achieved during deceleration between the monitoring systems
- Compare the degree of variability in the tracing between the monitoring systems. Degree of variability will be defined as the correlation between the tracings. The tracings will be broken down into 4 minute intervals and defined as minimal, moderate or marked variability and compared with each other for accuracy and

Version 5.13; June 19, 2020

consistency. Most accurate will be the internal monitor in each case, i.e. fetal scalp electrode.

- Compare patient satisfaction between the monitoring systems

Inclusion criteria:

- 1) Maternal age >18 years old
- 2) Singleton pregnancy
- 3) Gestational age of 24 completed weeks or greater based on the estimated due date as calculated from last menstrual period or early ultrasound
- 4) Category I (reassuring) fetal heart rate tracing at time of enrollment

Exclusion criteria:

- 1) Fetal anomaly or chromosome defect
- 2) Allergy to silver
- 3) Woman with implanted electronic device of any kind
- 4) Irritated skin or open wound on the abdominal wall

Recruitment Mechanisms:

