Because many of these patients will overlap due to the fact that they will serve as their own control and will be monitored simultaneously for fetal heart rate and change in cervical exam, it is anticipated that the maximum number of patients required in this study will not be more than 220 patients since 55 obese and 55 non-obese patients will be needed and additional patients may be needed to evaluate productive contractions. In addition to comparing the continuity in readings, in assessing contractions, we will also compare average frequency of contractions, the duration of contraction, maximum height of the contraction, the total Montevideo units obtained, the timing of the contraction and the amount of discontinuous tracings from the devices. In assessing fetal heart rate, we will compare average fetal heart rate, baseline heart rate, the number accelerations, the number of decelerations, the timing of the accelerations, the timing of decelerations, the maximum fetal heart rate achieved during acceleration, the lowest fetal heart rate achieved during deceleration, and compare the degree of variability in the tracing. A continuous outcome will be compared using a paired t-test.

Version 5.13; June 19, 2020

As each patient is serving as its own control, missing data is unlikely to be an issue in this study once the patient consents. If the monitoring is less than 30 minutes, these patients will not be used in analysis due to concern for completeness and accuracy.

Safety assessment:

Safety and tolerability will be assessed by recording of adverse events. Adverse events will be reported. Adverse events will be assessed in terms of their seriousness, severity, and relationship to the study device. To date more than 800 patients have used the device in clinical trials and there have been no safety events reported with the use of the device to date.

Potential benefits:

There is no immediate benefit to the subject from her participation in this study. The study results will support the development of the EUM300pro system, which may have clinical importance in providing the care provider with more continuous and accurate monitoring of fetal heart rate and contractions in a less invasive way. These parameters will aid the medical staff in making timely clinical decisions and increasing the chances of attaining a successful treatment and/or delivery.

Potential risks:

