No severe or serious events are anticipated with the use of the EUM300 system. There is a potential for an allergic reaction to the EUM adhesive.

Alternatives:

Patients may choose not to participate in the study or withdraw from the study at any time for any reason without compromise or change in their care.

Adverse Events:

Definition of Adverse Events (AE)

An AE is any reaction, side effect, or other untoward event (signs, symptoms, and changes in laboratory data) associated with the use of a test article (drug, biologic, or device),

Version 5.13; June 19, 2020

whether or not the event is considered related to the test article. All AE occurring after the administration of study treatments will be recorded. AE will be ascertained on the basis of volunteered symptoms and clinical observation and assessment at study visits. AE and concomitant medication information will be recorded during study visits on the appropriate case report form (CRF) page, and every effort will be made to capture information regarding AE and concomitant medications between visits. All AE considered to be related to study treatment, and all serious AEs (SAE) will be followed until resolved or until a stable status has been achieved.

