### Serious Adverse Events definition and reporting

Version 5.13; June 19, 2020

All serious adverse events require additional detailed reports and follow-up. A serious adverse experience is any adverse experience that is fatal or life-threatening, is permanently disabling, requires or prolongs inpatient hospitalization, or is a congenital anomaly, cancer, or the result of an overdose.

All serious adverse events, whether or not device related or expected, must be reported by the Investigator to the Sponsor within one working day by fax or E-mail (initial report). A written report, which includes a full description of the event, will be sent to the Sponsor within 5 working days. This includes serious adverse events that occur any time after the inclusion of the patient in the study until 30 days after using the study device.

Reports of SAEs related to the study device, will be evaluated and assessed by the sponsor's medical advisors.

All serious adverse events must be reported to the appropriate Institutional Review Board or ethical committee in accordance with local laws and regulations.

Removal of a subject from the study due to adverse experiences whether by the Investigator or by the subject's own volition, should be reported promptly to the Medical Monitor.

Studies completed using EUM:

Version 5.13; June 19, 2020

---

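### The under-30-minutes exclusion drops whole patients and does not exempt the satisfaction survey, which tilts that comparison towards EUM; no denominator for adverse-event rates is stated

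*Combined protocol and SAP*

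**What the plan says.** The rule closes the Statistics section, just before Safety assessment: "If the monitoring is less than 30 minutes, these patients will not be used in analysis due to concern for completeness and accuracy." The sentence before it states that "missing data is unlikely to be an issue in this study once the patient consents." No other analysis set is defined in the document.

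Satisfaction is the last of the 15 secondary outcomes under Materials and Methods: "Compare patient satisfaction between the monitoring systems." The data come from a device experience and satisfaction survey. No survey timing, scale or analysis set is given, and nothing says how women who stop early are handled.

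Safety has its own text. Safety assessment says: "Safety and tolerability will be assessed by recording of adverse events. Adverse events will be reported." Adverse Events says: "All AE occurring after the administration of study treatments will be recorded." Potential risks names one device harm: "There is a potential for an allergic reaction to the EUM adhesive." Alternatives allows withdrawal at any time, and the section on serious adverse events asks for prompt reporting of "Removal of a subject from the study due to adverse experiences whether by the Investigator or by the subject's own volition." None of these provisions depends on 30 minutes of monitoring, and none states the denominator for an adverse-event rate.

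**The concern.** The reason given for the rule, completeness and accuracy, suits a comparison of 30-minute tracings. It does not suit a survey response, which is just as valid after 10 minutes of wear as after 30. Yet the rule is worded for patients and for analysis in general.

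A woman who removes the patch early because it itches or is uncomfortable is among those most likely to rate EUM poorly. Her exclusion is then caused by the quantity being compared. Pairing does not protect against this: each woman is her own control, but the women left are selected on their opinion of one of the two devices. At stake are a listed secondary outcome and, less directly, a clear base for any adverse-event percentage.

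**Working it through.** The plan states no figure on this point, so there is none to reproduce. The check is a reading of the text followed by an illustration on assumed values.

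**1. Which outcomes does the rule reach?**

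| Outcome | Needs 30 minutes of signal? | Exempted from the rule? | Other provision |
|---|---|---|---|
| Tracing comparisons | Yes, 30-minute samples are compared | No | None needed |
| Satisfaction survey | No | No | None |
| Adverse events | No | Not expressly | Recorded and reported with no minimum time; denominator not stated |

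The literal rule therefore bears on satisfaction. For adverse events it leaves only the denominator open.

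**2. Size for satisfaction.** Let *f* be the fraction of women who stop before 30 minutes because of discomfort or a reaction, and *m* their mean EUM-minus-standard score. If the true mean over all women is 0, then *f·m* + (1 − *f*)·(mean of the rest) = 0, so the mean of the rest is −*m·f*/(1 − *f*).

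Assumed, because the plan gives none of these: *m* = −4 on a 10-point scale, and *f* = 2%, 4% or 6%. The Statistics section caps enrolment at 220.

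| *f* | Women removed at the cap, 220 × *f* | Apparent mean difference, 4*f*/(1 − *f*) |
|---|---|---|
| 2% | 4.4 | 0.08/0.98 = +0.08 |
| 4% | 8.8 | 0.16/0.96 = +0.17 |
| 6% | 13.2 | 0.24/0.94 = +0.26 |

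The shift is proportional to the assumed deficit. Its direction needs only that early stoppers rate EUM lower, relative to standard monitoring, than the other women do. Women who fall short of 30 minutes for unrelated reasons, such as delivery or discharge, are not part of *f*. The rule does not separate these reasons, nor does it say whether the EUM or the standard monitor must reach 30 minutes.

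**3. What the missing denominator could do.** Suppose a further 2% of all women have an event after 30 minutes (assumed). The same records then support three different percentages:

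| *f* | All events over all women with electrodes applied, *f* + 2% | All events over women with at least 30 minutes, (*f* + 2%)/(1 − *f*) | Later events only, over women with at least 30 minutes, 2%/(1 − *f*) |
|---|---|---|---|
| 2% | 4.0% | 4.1% | 2.0% |
| 4% | 6.0% | 6.3% | 2.1% |
| 6% | 8.0% | 8.5% | 2.1% |

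The first two columns agree with recording and reporting every event, and they differ little. The third requires early events to be left out of the report, which the plan does not say.

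**The case against.** **The rule is about tracings.** It follows a list of contraction and heart-rate comparisons, speaks of monitoring, and gives a reason that fits signal data. This is probably what the authors meant. It stands as a reading of intent, but the sentence excludes patients and exempts nothing, so an analyst who follows it literally would drop the survey responses too.

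**Tolerability is covered elsewhere.** A reader might infer that tolerability would be estimated only in women who tolerated the device. The documents do not support that. All adverse events after application are recorded, adverse events are reported, and removals for adverse experiences go to the Medical Monitor, with no 30-minute condition on any of these. Materials and Methods also keeps the electrodes on until delivery or discharge, so women who react after 30 minutes stay in the analysis. This objection stands in full; only the denominator is left open.

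**Early intolerance may be rare.** Safety assessment reports more than 800 earlier users without a safety event. Zero of 800 has an exact two-sided 95% upper limit of 1 − 0.025^(1/800), about 0.46%, or about 1 woman in 220. Women with silver allergy or with irritated or broken abdominal skin are excluded. At *f* = 0.46% the shift would be 4 × 0.0046/0.9954, about 0.02 points. This carries weight, although safety events may not include the mild discomfort that leads a woman to remove a patch.

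**Changing the analysis set may recover nothing.** A woman who withdraws may never fill in the survey, and its timing is not given. This stands, and it is why early stoppers have to be asked for the survey.

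**Conclusion.** The point holds for satisfaction. Read as written, the rule removes early stoppers from that comparison for a reason related to the outcome, and the tilt is towards EUM. The direction rests on one assumption, that women who stop for discomfort or a skin reaction rate EUM lower than the others do. The size cannot be derived from the documents. On the assumed values it is 0.08 to 0.26 points on a 10-point scale, and it would be nearer 0.02 if early stopping were as rare as the upper limit from the earlier users. A small effect on one secondary outcome is the likeliest case.

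For adverse events, the finding is only that no denominator is stated. Early events are not lost under the plan as written. The tracing outcomes, including both primary outcomes, are outside this point.

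**What to change.** Amend the Statistics section to say that:

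- the under-30-minutes exclusion applies to the tracing comparisons only, naming which monitor's duration counts;
- satisfaction is analysed in every woman who had EUM electrodes applied and completed the survey, whatever the length of monitoring, and women who stop early are asked to complete it;
- adverse events are reported over all women to whom electrodes were applied;
- the number monitored for under 30 minutes is reported with reasons, separating discomfort or skin reaction from delivery, discharge and technical failure.

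The cost is a few lines of text, one request to early stoppers and a recorded reason for stopping. No extra patients are needed. The satisfaction and safety denominators will differ from the tracing denominator and must be shown separately. Early stoppers who decline the survey will still be missing from the satisfaction comparison, so their number should be stated beside it.

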### Relationship

The relationship between an AE and the study intervention will be determined by the Investigator on the basis of his or her clinical judgment and the following definitions:

- Associated: There is a reasonable possibility that the AE may have been caused by the study device. This definition applies to those AEs that are considered definitelya, probablyb, and possiblyc related to the use of the study device.
  - a. Likely Related: An AE that: follows a reasonable temporal sequence from using the study device; follows a known response pattern to the study device; and, when appropriate to the protocol, is confirmed by improvement after stopping the study device (positive dechallenge) and by reappearance of the reaction after repeat exposure (positive rechallenge); and cannot be reasonably explained by known characteristics of the participant's clinical state or by other therapies.
  - b. Probably Related: An AE that: follows a reasonable temporal sequence from administration of the study device; follows a known response pattern to the study device; and, when appropriate to the protocol, is confirmed by improvement after dechallenge; and cannot be reasonably explained by the known characteristics of the participant's clinical state or by other therapies.
  - c. Possibly Related: An AE that: follows a reasonable temporal sequence from administration of the study device and follows a known response pattern to the study device but could have been produced by the participant's clinical state or by other therapies.

Version 5.13; June 19, 2020

- Not Related: An AE for which sufficient information exists to indicate that the etiology is unrelated to the study device. Two or more of the following variables apply:
  - a. The AE does not follow a reasonable temporal sequence after administration of the study device.
  - b. The AE is readily explained by the participant's clinical state or other therapies.
  - c. Negative dechallenge - the AE does not abate upon dose reduction or cessation of therapy (assuming that it is reasonable to expect abatement of the AE within the observed interval).

### Severity

The intensity of an AE will be assessed as follows:

- None
- Mild: does not interfere with routine activities, can perform daily functions
- Moderate: interferes with routine activities, can perform daily functions, but with concerted effort
- Severe: participant is unable to perform routine activities

### Outcome

The outcome of an AE will be assessed as follows:

- Resolved
- Unresolved
- Resolved with sequelae
- Worsening
- Death

### Serious Adverse Events definition and reporting

Version 5.13; June 19, 2020

All serious adverse events require additional detailed reports and follow-up. A serious adverse experience is any adverse experience that is fatal or life-threatening, is permanently disabling, requires or prolongs inpatient hospitalization, or is a congenital anomaly, cancer, or the result of an overdose.

All serious adverse events, whether or not device related or expected, must be reported by the Investigator to the Sponsor within one working day by fax or E-mail (initial report). A written report, which includes a full description of the event, will be sent to the Sponsor within 5 working days. This includes serious adverse events that occur any time after the inclusion of the patient in the study until 30 days after using the study device.

Reports of SAEs related to the study device, will be evaluated and assessed by the sponsor's medical advisors.

All serious adverse events must be reported to the appropriate Institutional Review Board or ethical committee in accordance with local laws and regulations.

Removal of a subject from the study due to adverse experiences whether by the Investigator or by the subject's own volition, should be reported promptly to the Medical Monitor.

Studies completed using EUM:

Version 5.13; June 19, 2020

---

## Option 1 – normal EUM300 setup

AFE – Analog Frontend

DSP – Digital Signal Processing board

[figure not shown]
BT – Bluetooth

LAN – Local Area Network

RS232 – Industry standard HP-50 Communication protocol

UA – Uterine activity  
FHR – Fetal Heart Rate

### Option 2 - EUM300 with dedicated notebook

The proposed setup eliminates the need to install the interface unit during the clinical evaluation time frame and minimize the required changes to the delivery room setup. The maternal unit will transmit the uterine activity/fetal heart rate information to an off-the-shelf computer equipped with Bluetooth V4.0 (e.g., Lenovo IdeaPad U41-70). An existing fetal monitor transmits similar information using HP-50 protocol over RS232 physical connection. The RS232 is likely to be connected to existing hospital IT. A simple Y connection is the only change needed to the delivery room. The RS232 transmissions will also be received by an off-the-shelf USB-RS232 adaptor.

Version 5.13; June 19, 2020

---

A computer program will record both the EUM300 and the fetal monitor into a common file (CSV format in order to be able to be analyzed by either Matlab or Excel). Program may also present the four signals (EUM Uterine, EUM FHR, monitor Uterine, monitor FHR) in real time. Other features may be: Dialog to provide the file information with patient ID, name, gestational age, etc.
